---

## PROTOCOL SYNOPSIS

---

### An open label Positron Emission Tomography (PET) study with (S,S)[F]FMeNER-D2 to determine central norepinephrine transporter occupancy of quetiapine (SEROQUEL SR™) in healthy male volunteers

---

#### Study centre(s), type and number of subjects planned

[REDACTED]

[REDACTED] It is planned to include six to nine healthy male volunteers, aged 20-45 years.

#### Study period

Estimated date of first subject enrolled

[REDACTED]

Estimated date of last subject completed

[REDACTED]

#### Phase of development

Phase 1

#### Objectives

The primary objectives are:

- to determine the occupancy of norepinephrine transporter (NET) induced by Seroquel (SQL) at doses of SEROQUEL SR™ currently evaluated in the clinical program for Major Depressive Disorder
- to determine the relationships: 1) between SQL dose at close to steady state condition and NET occupancy; 2) between plasma concentrations of quetiapine, its main active metabolite N-desalkyl-quetiapine (NDAQ) and NET occupancy

The secondary objectives of the study are:

1. to characterize the pharmacokinetics of quetiapine and its metabolite NDAQ in the subjects undergoing PET analysis
2. to assess adverse events (AEs), vital signs and changes in laboratory parameters and Bond- Lader VAS (Bond et al 1974)

### **Study design**

This is an open-label, non-randomised, single centre study using positron emission tomography (PET) in six to nine healthy volunteers, aged 20-45 years, to determine central NET occupancy induced by SEROQUEL SR™ (SQL SR). For each healthy volunteer, titration and maintenance dosing of SQL SR will be used over four to eight days. The healthy volunteers will be confined to the CPU during titration and maintenance dosing of SQL SR. Each healthy volunteer will be examined by PET at two separate occasions, at baseline (no medication) and at close to steady state of chosen SQL SR dose. In the two PET examinations a tracer amount of the radioligand (S,S)[F]FMeNER-D2 will be given. The study will be concluded by a follow-up visit at the CPU five to nine days after the last SQL SR dose.

### **Investigational product, dosage and mode of administration**

For each healthy volunteer, titration and maintenance dosing of SQL SR will be used over four to eight days. SQL SR will be titrated increasingly from 50 mg per day and, if tolerated, to the target dose of 300 mg/day in Panel A. In Panel B the SQL SR maintenance dose will be selected to complete the information obtained in Panel A and may be chosen in the range from 50 to 300 mg/day. A third Panel may be added if judged necessary. The SQL SR dose will be administered orally, as a solid dosage form. Intact tablets will be swallowed with 240 mL of water.

Serial blood samples will be obtained from each healthy volunteer for 24 hours at the day for PET examination 2. The samples will be analysed for plasma concentrations of quetiapine and NDAQ.

In the present study (S,S)[F]FMeNER-D2 will be synthesized by the radio chemists at the PET centre from a precursor immediately before intravenous administration. The total radioactivity will be maximum 375 MBq (approximately 185 MBq per injection), mass of radioligand injected will not exceed 5 micrograms per subject per injection (calculated from 0.07µg/kg body weight, 70 kg).

### **Duration of treatment**

Each healthy volunteer in Panel A will receive eight doses of SQL SR and two single doses of the radioligand (S,S)[F]FMeNER-D2.

## **Variables**

### **- PET pharmacokinetics**

The regional uptake and distribution of (S,S)[F]FMeNER-D2 in regions of interest (ROI) in the brain, following a single intravenous dose will be assessed. Regional radioactivity uptake, presented as time-activity curves (TAC), and derived variable, binding potential (BP), will be used for the calculations of primary endpoints.

### **- SQL pharmacokinetics**

The following steady-state pharmacokinetic variables will be determined for quetiapine, N-desalkyl-quetiapine;  $C_{ss,max}$ ,  $C_{ss,min}$ ,  $t_{max}$ ,  $AUC_{ss}$ ,  $AUC(0-t)$  and  $t_{1/2}$ .

The following pharmacokinetic parameter will be determined for quetiapine alone: CL/F apparent oral clearance

### **- Safety**

Adverse events, vital signs, ECG, clinical chemistry, haematology and urinalysis, Bond-Lader VAS.

### **- Statistical methods**

The statistical analysis will be descriptive and exploratory. The safety, tolerability, and pharmacokinetic variables will be analysed using subject listings and summary statistics.

Exploratory analyses will be made of the relationships between dose, plasma concentration of quetiapine and NDAQ, and NET occupancy through nonlinear statistical modelling.

	PAGE
TITLE PAGE .....	1
PROTOCOL SYNOPSIS .....	3
TABLE OF CONTENTS .....	6
LIST OF ABBREVIATIONS AND DEFINITION OF TERMS .....	10
1. INTRODUCTION .....	12
1.1 Background .....	12
1.2 Rationale .....	13
2. STUDY OBJECTIVES .....	14
2.1 Primary objective .....	14
2.2 Secondary objective(s) .....	14
3. STUDY PLAN AND PROCEDURES .....	14
3.1 Overall study design .....	14
3.1.1 Stopping criteria for dose escalation .....	16
3.2 Rationale and risk/benefit assessment .....	21
3.2.1 Rationale for study design, doses and control groups .....	21
3.2.2 Risk/benefit and ethical assessment .....	22
3.3 Selection of study population .....	23
3.3.1 Study selection record .....	23
3.3.2 Inclusion criteria .....	24
3.3.3 Exclusion criteria .....	24
3.3.4 Restrictions .....	25
3.3.5 Discontinuation of subjects from treatment or assessment .....	26
3.3.5.1 Criteria for discontinuation .....	26
3.3.5.2 Procedures for discontinuation .....	27
3.3.5.3 Procedures for handling incorrect enrolled subjects .....	27
3.4 Treatment(s) .....	27
3.4.1 Investigational product(s) .....	27
3.4.1.1 Identity of investigational product .....	27
3.4.1.2 Labelling .....	28
3.4.1.3 Storage .....	29
3.4.1.4 Accountability .....	29
3.4.2 Doses and treatment regimens .....	29
3.4.2.1 Light meal .....	30
3.4.2.2 Other meals .....	31
3.4.3 Method of assigning subjects to treatment groups .....	31
3.4.4 Concomitant medication .....	31

3.4.5	Treatment compliance.....	31
4.	MEASUREMENT OF STUDY VARIABLES .....	31
4.1	Medical examination and demographic measurements .....	31
4.1.1	Enrolment medical examination and demographic measurements.....	31
4.1.2	Post-study medical examination .....	32
4.2	Pharmacokinetic measurements.....	32
4.2.1	Determination of drug concentration in biological samples .....	32
4.2.2	Collection of biological samples.....	32
4.2.3	Labeling of plasma samples.....	33
4.2.3.1	Shipment of SQL SR plasma samples .....	33
4.2.3.2	MRI examination .....	34
4.2.3.3	PET examination.....	34
4.3	Pharmacodynamic measurements (Not applicable).....	35
4.4	Safety measurements .....	35

## LIST OF ABBREVIATIONS AND DEFINITION OF TERMS

The following abbreviations and special terms are used in this study protocol.

Abbreviation or special term	Explanation
AE	Adverse event
AUC PET	Area under plasma concentration-time curve corresponding to the PET-assessment planned at 5 to 7 hr post-dose
BMI	Body mass index
BP	Binding potential
C av,PET	Average plasma concentration during the PET-assessment planned at 5 to 7 hr post-dose.
C max	Maximum (peak) plasma drug concentration
CRF	Case report form
CPU	Clinical Pharmacology Unit
DMP	Data Management Plan
EC 50	Plasma drug concentration corresponding to 50% occupancy of NET
ECG	Electrocardiogram
ED	Effective dose, parameter evaluation risk from radiation exposure
ED 50	Dose of drug inducing 50% occupancy of NET
Ethics Committee	Synonymous to Institutional Review Board and Independent Ethics Committee
Euratom	European Atomic Energy Community
FDA/RDRC	Federal Drug Agency: Radioactive Drug Research Committee
GAD	Generalised Anxiety Disorder
GCP	Good Clinical Practice
HBA	Human Brain Atlas
HBV	Hepatitis B virus
HCV	Hepatitis C virus
HIV	Human Immunodeficiency virus
ICH	International Conference on Harmonisation
IR	Immediate release
IRB	Institutional Review Board
[REDACTED]	[REDACTED]

Abbreviation or special term	Explanation
[REDACTED]	[REDACTED]
LSD	Lysergic acid diethylamide
MDD	Major Depressive Disorder
MRI	Magnetic Resonance Imaging
NET	Noradrenaline (norepinephrine) transporter
NDAQ	N-desalkyl-quetiapine (AZ10081909)
OAE	Other Significant Adverse Event (ie, adverse events of particular clinical importance, other than SAEs and those AEs leading to discontinuation of the subject from study treatment; see definition in Section 4.7.1.1).
PD	Pharmacodynamics
PET	Positron Emission Tomography
PK	Pharmacokinetics
Principal investigator	A person responsible for the conduct of a clinical study at a study site. Every study centre has a principal investigator.
ROI	Region of Interest
SAE	Serious adverse event
SQL	Seroquel
SR	Sustained release
(S,S)[  F]FMeNER-D 2	(S, S)-2-( $\alpha$ -(2-methoxyphenoxy)benzyl)morpholine
SUV	Standard uptake values
TAC	Time-activity curve
T max	Time to reach maximum drug plasma concentration
T 1/2	The terminal elimination half-life
VAS	Visual Analogue Scale
WHO	World Health Organisation

## 1. INTRODUCTION

### 1.1 Background

Quetiapine fumarate (SEROQUEL™) (SQL) is a benzodiazepine derivative that is designated clinically as 2-(2-[2-(4-dibenzo[b,f] [1,4]thiazepin-11-yl-1 piperazinyl)ethoxy]-ethanol] fumarate (2:1). This atypical antipsychotic was developed by AstraZeneca and was first licensed by the UK Medicines and Healthcare products Regulatory Agency (MHRA) in July 1997 and by the US Food and Drug Administration (FDA) in September 1997 for the treatment of schizophrenia. Following this, SQL was approved in Europe in October 2003 and in the US in January 2004 for the treatment of bipolar mania and in November 2006 for the treatment of depression associated with bipolar disorder. Currently, SQL immediate-release (IR) tablets are administered 2 times daily and with a recommended 4-day treatment-initiation period to reach the target therapeutic dose.

[REDACTED] AstraZeneca has filed a new Submission for a sustained-release (SR) formulation, SEROQUEL SR™, in 2006 in several countries (including the US and Europe) for the management of the manifestations of schizophrenia. The dossier includes 20 completed studies: 7 biopharmaceutical (pharmacokinetic) studies, 6 clinical pharmacology (pharmacodynamic) studies, 5 efficacy and safety studies (covering 3 clinical settings: acute exacerbation of schizophrenia, relapse prevention, and switching from SQL IR to SQL SR under stable disease conditions) and 2 other studies. The efficacy and safety studies included more than 2400 patients with schizophrenia, more than 1500 of whom were treated with SQL SR. The biopharmaceutical and clinical pharmacology studies included approximately 300 additional patients with schizophrenia, schizoaffective disorder, or bipolar disorder who were treated with SQL SR. The submissions are currently under review.

SQL SR is [REDACTED] available as 50 mg, 200 mg, 300 mg, and 400 mg tablets, which have undergone a full program of pharmacokinetic evaluation ([Investigator's Brochure, SEROQUEL™, 2007](#)). SQL SR is a sustained-release formulation with a predictable and reproducible pharmacokinetic profile, designed to be administered once daily. Peak plasma quetiapine concentrations ( $C_{max}$ ) occur approximately 6 hours after administration of quetiapine SR ( $t_{max}$ ), compared with approximately 1 hour for the IR formulation. The elimination half-life of quetiapine is approximately 7 hours for both formulations. SQL SR displays dose-proportional pharmacokinetics for doses of up to 800 mg administered once daily. When compared directly to the same total daily dose of SQL IR administered in divided doses twice daily to steady state, SQL SR administered once daily displays the same area under the plasma concentration-time curve (AUC), and  $C_{max}$  for SQL SR is approximately 13% lower than that observed for the morning dose of SQL IR. A high-fat meal (approximately 800 to 1000 calories, with 50% derived from fat content) produced significant increases in  $C_{max}$  (44% to 52%) and AUC (20% to 22%). In comparison, a light meal (approximately 300 calories, with minimal fat content) had no significant effect on the  $C_{max}$  or AUC of SQL SR.

In an attempt to expand the treatment options currently available for the treatment of Major Depressive Disorder (MDD) and to build upon existing clinical data observed with SQL IR, AstraZeneca is exploring the use of SQL SR within the dose range 50 to 300 mg/day as a treatment of MDD in a number of clinical studies. AstraZeneca is conducting eight Phase III clinical studies to assess safety and efficacy of SQL SR in the treatment of MDD. The clinical development programme consist of four monotherapy studies, two adjunct studies, one study within the elderly population, and one study assessing the effectiveness of SQL SR in increasing the time to relapse of depression.

Both SQL IR and SQL SR have been studied in clinical programs directed at supporting clinical evaluation in man. The results of these studies may be found in the SEROQUEL™ Investigator's Brochure, 2007.

## 1.2 Rationale

Antidepressant activity of SQL IR has been suggested from anecdotal reports, case studies, and small published and unpublished studies in patients with MDD. In patients with schizophrenia, SQL IR has been shown to improve depressive symptoms independently of their effect on psychotic symptoms (Emsley et al 2003). Recent data, from two large randomized placebo-controlled studies utilizing SQL IR as monotherapy in the treatment of bipolar depression, showed SQL IR to be effective in treating depression associated with bipolar disorder (Calabrese et al 2005).

The neurochemical profile of SQL has been investigated in non-human primates and human PET experiments. It has been shown that active substance quetiapine and major metabolite N-desalkyl-quetiapine (NDAQ) has high to moderate affinity to several central neuroreceptors, including dopamine D2, D1, serotonin 5-HT1A, 5HT2 receptors, serotonin transporter, 5HTT (5077CN-0021, 2003, D2200C00011, 2006, Gefvert et al 1998). Based on the *in vitro* binding profile and initial Positron Emission Tomography (PET) study on non-human primates it is predicted that quetiapine/NDAQ may in addition have affinity to norepinephrine transporter (NET) *in vivo* in humans. Noradrenaline system is implicated in the pathophysiology of depression and anxiety disorders (Klimek et al 1997, Sullivan et al 1999).

In the present study relation between plasma concentrations of quetiapine and NDAQ and the occupancy of NET in male healthy volunteers will be investigated.

The selective radioligand (S,S)[F]FMeNER-D2 will be used for PET measurements of NET occupancy (Seneca et al 2005, Seneca et al 2006). PET measurements will yield endpoint – binding potential (BP) and its change in response to treatment with clinically relevant SQL SR doses. BP will be derived from the regional time-activity curves in the target region - thalamus and caudate nucleus as a reference region (i.e. region with negligible NET expression) (Seneca et al 2006).

SQL binding to the norepinephrine transporter in the human brain will be examined and dose-dependent NET occupancy will be determined.

## 2. STUDY OBJECTIVES

### 2.1 Primary objective

The primary objective of the study is:

- to determine the occupancy of NET induced by SQL at doses of SQL SR currently evaluated in the clinical program for MDD
- to determine the relationships: 1) between SQL dose at close to steady state condition and NET occupancy; 2) between plasma concentrations of quetiapine, its main active metabolite NDAQ and NET occupancy

### 2.2 Secondary objective(s)

1. to characterize the pharmacokinetics of quetiapine and its metabolite NDAQ in the subjects undergoing PET analysis
2. to assess adverse events (AEs), vital signs and changes in laboratory parameters and Bond- Lader VAS ([Bond et al 1974](#))

## 3. STUDY PLAN AND PROCEDURES

### 3.1 Overall study design

This Clinical Study Protocol has been subjected to a peer review according to AstraZeneca standard procedures.

This is an open-label, non-randomised, single centre, exploratory PET study in six to nine healthy volunteers, aged 20-45 years, to determine central norepinephrine transporter occupancy of SQL SR.

The study will be conducted as a research collaboration between AstraZeneca Clinical Pharmacology Unit (CPU), [REDACTED]

The study will consist of two to three panels that are performed sequentially. Each panel will have 3 healthy volunteers. In the starting panel, Panel A, the SQL SR maintenance dose will be 300 mg. This will be followed by an interim analysis. In Panel B the SQL SR dose will be selected to complement the information obtained in Panel A. A third Panel (C) may be added if judged necessary.

In Panel A, the healthy volunteers will be administered with SQL SR 50 mg for 2 days beginning at Day 1. Beginning at Day 3, the healthy volunteers will be administered SQL SR 150 mg for 2 days and beginning at Day 5 the healthy volunteers will be administered 300 mg

SQL SR for 4 days (maintenance dose). See [Figure 1](#) for a detailed presentation of SQL SR dosing and PET measurements in Panel A. In Panel B and C the titration period may be 0, 2 or 4 days depending on dose levels. Thus, depending on the panel, the total (titration and maintenance) dosing of SQL SR for an individual healthy volunteer may be from four to eight days. The healthy volunteers will be confined to the CPU during titration and maintenance dosing of SQL SR, with close monitoring of vital signs (pulse, systolic and diastolic blood pressure) and adverse events (see [Table 1](#)). The total length of participation for a healthy volunteer, including screening and follow-up procedures, is a max of 50 days.

Initially, healthy volunteers will undergo a medical examination (see section [4.1.1](#)) at the CPU to determine eligibility criteria. Suitable healthy volunteers will be referred to the magnetic resonance imaging (MRI) centre at [REDACTED] to obtain MRI scans, that will verify absence of pathology in the brain and will be used in the analysis of PET data, for the detailed anatomical delineation of regions of interest (ROIs).

Thereafter, each healthy volunteer will undergo two PET examinations at two separate occasions at the [REDACTED]. The first PET examination is a baseline assessment of the distribution and density of noradrenaline transporter in the brain. After that, healthy volunteers will be confined to the AstraZeneca CPU during all days of SQL SR dosing, one of the days will also include a second visit to the PET centre. The second PET examination will be performed under SQL SR dosing (maintenance dose). The study will be concluded by a follow-up visit at the CPU five to nine days after the last SQL SR dose.

On the PET 2 examination the timing of the PET examination will be matched with the known PK parameters, median  $T_{max}$  of quetiapine and NDAQ after oral administration of SQL SR at 6 hours post-dose. For this reason the radioligand will be administered tentatively 3 and a half hours after administration of SQL SR and PET scanning time will be at 5-7 hours post-dose. A light meal (breakfast) approximately 2 hours prior to SQL SR administration will be given and a light meal will be given at 4 hours post dose. Monitoring of vital signs will be performed, prior to SQL SR intake.

In the unexpected event of technical failure (camera breakdown or the radioligand synthesis fails), the PET examination has to be moved to the nearest working day. In this case the SQL SR maintenance dosing period will be prolonged by 1-3 days (three days if it is moved from Friday to Monday). If this occurs the time the healthy volunteer are confined to the CPU will be prolonged.

Twelve serial blood samples will be obtained from each healthy volunteer between 15 min before administration of SQL SR and up to 24 hr after drug administration, at the second PET examination. The samples will be analysed for plasma concentrations of quetiapine and NDAQ. The aim is to take one sample at the start of the PET examination, one in the middle and one at the end of the PET examination.

### **3.1.1 Stopping criteria for dose escalation**

Daily doses of SQL SR, will be administered sequentially during the inpatient treatment portion of the study (Days 1 through 8 for Panel A). The titration scheme will progress to the next higher dose unless otherwise agreed by the Principal Investigator and sponsor to stop due to potentially clinically significant vital signs and safety laboratory measurements and/or clinically significant adverse events.

**Table 1 Study plan**

Visit	1	2	3	4	Residential period			5	
Visit Description	Enrolment	MRI Scana	PET Exam1a	Admission to CPU	SQL SR titration	SQL SR maintenance	PET Exam 2 after SQL SR dose	Discharge Follow-up	
Visit Window (Day)	Within -30 to -4 days	Within -29 to -1 days	Within -7 to -1 days	Day -1	Day 1-4b	Day 5-7b,c	Day 8	Day 9	5-9 days after last dose
Informed consent	X								
Demographic measurements	X								
Medical/surgical history	X								
Physical and neurological examination	X								X
Habits of nicotine, alcohol and caffeine	X								
Vital signs d	X				X e	X e	X	X	X
Electrocardiogram	X			X f		X g		X	
Inclusion/exclusion criteria	X								

Visit	1	2	3	4	Residential period			5
Visit Description	Enrolment	MRI Scan a	PET Exam1a	Admission to CPU	SQL SR titration	SQL SR maintenance	PET Exam 2 after SQL SR dose	Discharge Follow-up
Visit Window (Day)	Within -30 to -4 days	Within -29 to -1 days	Within -7 to -1 days	Day -1	Day 1-4b	Day 5-7 b,c	Day 8	Day 9
								5-9 days after last dose
Clinical chemistry/Haematology	X			X h				X
Urinalysis	X			X h				
Hepatitis B, C, and HIV	X							
Drugs of abuse screen	X							
Production of plaster helmet			X					
MRI		X						
PET after iv administration of (S,S)[18F]FMeNER-D2			X				X i	
Administration of SQL SR once daily in the morning					X	X	X	
Blood sampling for quetiapine PK							X j	

Visit	1	2	3	4	Residential period			5
Visit Description	Enrolment	MRI Scan a	PET Exam 1a	Admission to CPU	SQL SR titration	SQL SR maintenance	PET Exam 2 after SQL SR dose	Discharge Follow-up
Visit Window (Day)	Within -30 to -4 days	Within -29 to -1 days	Within -7 to -1 days	Day -1	Day 1-4b	Day 5-7 b,c	Day 8	Day 9
								5-9 days after last dose
Bond- Lader VAS k				X l	X	X	X	X
Adverse events m				X	X	X	X	X

- a) MRI and PET examination 1 cannot be done on the same day.
- b) In panel B and C the titration period may be removed (i.e. if dose is set to 50 mg) or changed to two days (i.e. if dose is set to 150 mg). The range of total time at CPU may thus be from 6 to 10 days for panel B and C.
- c) In the unexpected event of technical failure (camera breakdown or the radioligand synthesis fails), the PET examination has to be moved to the nearest working day. Then it is done during the nearest days. In this case the SQL SR maintenance dosing period will be prolonged by 1-3 days (three days if it is moved from Friday to Monday). If this occurs the time the healthy volunteers are confined to the CPU will be prolonged.
- d) Vital signs includes pulse, systolic and diastolic blood pressure supine and again 2 min after standing.
- e) Vital signs will be assessed pre-dose and 6 hours post-dose during SQL treatment days, except for the PET 2 examination day, when vital signs will be assessed only pre-dose.
- f) ECG should be assessed prior to first titration dose, either day -1 or day 1.
- g) ECG should be assessed 6 hours post-dose the third day of steady state (maintenance dose).
- h) Blood sampling for a reduced Clinical chemistry/Haematology and Urinalysis should be repeated on the day of admission to the CPU if these samples were taken (at Enrolment visit) more than 1 week ago.
- i) Radioligand (S,S) [F]F MeNER-D2 to be injected 3.5 h (210 min) post-SRQ SR dose.  
PET measurements to start approximately 5 h post-SQL SR dose.
- j) Venous blood for PK analysis are to be taken 15 min pre-SQL SR dose, and 1, 2, 3, 4, 5, 6, 7, 8, 10, 12 and 24 h post-SQL SR dose.
- k) Bond-Lader VAS should be in the morning pre-dose.
- l) Training –Bond-Lader VAS
- m) Adverse Events (AEs) must be recorded from the admission to the CPU and until the follow up visit. Serious Adverse Events (SAEs) must be recorded from the time when the informed consent is obtained until the follow-up visit.

[figure not shown]

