**During PET examination day**

**3.2 Rationale and risk/benefit assessment**

**3.2.1 Rationale for study design, doses and control groups**

In a study where the primary objective is to determine the occupancy of NET induced by quetiapine an open study is deemed sufficient.

The present study will be conducted in healthy male volunteers. The PET study requires to be performed in antipsychotic treatment-naïve subjects. Since patients requiring anti-psychotic therapy can rapidly destabilise and may have a relapse of symptoms when their anti-psychotic medication is stopped during the medication washout periods, it is considered inappropriate to

enrol such patients. Moreover it is also considered inappropriate to treat them with the SR doses proposed in this study, as they were not evaluated in the clinical program of SQL SR in patients with schizophrenia. Previous AstraZeneca studies have not shown any differences in pharmacokinetics of quetiapine between healthy and patient populations. Thus, it is presumed that NET occupancy of quetiapine in healthy volunteers will be representative of its binding to NET in human brain in vivo. Furthermore as many Central Nervous System (CNS) disease states to be studied with SQL SR will occur in antipsychotic treatment-naïve patients, healthy volunteers are thought to serve as an appropriate surrogate for the first study determining NET occupancy in man.

The doses that will be explored are those currently being evaluated in the MDD clinical program, 50 mg to 300 mg. The safety and tolerability of the doses selected in the present study and of a previous slightly quicker dose escalation scheme than currently proposed have been previously characterised in healthy volunteers and in patients with schizophrenia, schizoaffective disorder and bipolar disorder ([Investigator's Brochure, SEROQUEL™, 2007](#)). Necessary precaution to ensure the safety of the healthy volunteers will be taken (see 3.2.2). The PK characteristics of the doses chosen have also been characterized in healthy volunteers and/or in patients ([Investigator's Brochure, SEROQUEL™, 2007](#)): plasma quetiapine concentration time-profiles at oral doses of 50 mg, 150 mg and 300 mg: median time of  $C_{max}$ ,  $T_{max}$  is 6 hours,  $T_{1/2}$  is 6 hours post-dose. Plasma NDAQ concentration time-profiles:  $C_{max}$ , reaches  $T_{max}$  at 6 hours post-dose ([Investigator's Brochure, SEROQUEL™, 2007](#)).

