## Subjects in Panel A

The healthy volunteers will be administered with SQL SR 50 mg tablets once daily in the morning at the same time point for 2 days beginning at Day 1. Beginning at Day 3, the subjects will be administered SQL SR 3 x 50 mg tablets once daily in the morning (150 mg) for 2 days. At Day 5, SQL SR 300 mg tablets once daily in the morning will be administered for 4 days.

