#### **4.4.4 Bond-Lader Visual Analog Scale (VAS)**

This psychometric test will be collected at the times given in Table 1 to assess self-rated feelings. The first assessment upon admission to the CPU will be a training session to overcome practice effects and ensure optimal performance for the following assessments, which will take place pre-dose on the days of dosing of SQL SR and the day of discharge from the CPU. The second assessment on Day 1 (pre-dose) will be the baseline assessment.

The test being used for this study consists of a total of 16 100-mm lines anchored at either end by antonyms (Bond et al 1974). Participants mark their current subjective state between the antonyms on the line. Each line is scored as millimetres to the mark from the negative antonym.

The scale has a set of opposing adjectives at either end, as listed below:

alert – drowsy, calm–excited, strong–feeble, muzzy–clear headed, well-coordinated–clumsy, lethargic–energetic, contented–discontented, troubled–tranquil, mentally slow–quick witted, tense–relaxed, attentive–dreamy, incompetent–proficient, happy–sad, antagonistic–amicable, interested–bored, withdrawn–gregarious

At the specified time points during the study, subjects are asked to record how they feel at that time by making a vertical mark on the lines. Standardized instructions will be given to each subject before he completes the questionnaire. Study site personnel will check that the scale has been completed by the subject when collecting the questionnaire. The questionnaires will be evaluated using the same ruler for each subject. Date and time of collection and the distance from beginning of the line and the mark made by the subject on the VAS scale will

be recorded in mm in the CRF. If the mark occurs in between two hash marks on the ruler, the more conservative distance, ie, the longer distance will be recorded in the CRF.

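### Every on-drug Bond-Lader VAS is taken about 22-24 h after the previous tablet, so the scale can show only residual next-morning effect and not effect near the 6 h peak

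*Protocol*

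**What the plan says.** Footnote k of Table 1 states "Bond-Lader VAS should be in the morning pre-dose", and footnote d of Table 2 repeats this for the PET 2 day. Table 2 has no VAS entry at or after dosing. Section 4.4.4 describes the ratings that follow the training session as ones "which will take place pre-dose on the days of dosing of SQL SR and the day of discharge from the CPU". It also fixes the reference point: "The second assessment on Day 1 (pre-dose) will be the baseline assessment". The amendment reissues both tables and leaves the VAS timing unchanged.

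Panel A volunteers take their first tablets "once daily in the morning at the same time point for 2 days beginning at Day 1", and later dose levels are also given once each morning. Section 1.1 says that peak quetiapine concentrations "occur approximately 6 hours after administration of quetiapine SR".

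Other measures follow that peak:
- Footnote e of Table 1: "Vital signs will be assessed pre-dose and 6 hours post-dose during SQL treatment days", with the PET 2 day excepted (pre-dose only).
- Footnote g of Table 1: the maintenance ECG is at 6 h post-dose on the third maintenance day.
- Section 3.1: PET 2 scanning is at 5-7 h, chosen to match the median Tmax of quetiapine and NDAQ.

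Change in Bond-Lader VAS is part of secondary objective 2 (Section 2.2), and Section 6.2.1 lists the scale among the safety and tolerability variables. No section gives a reason for rating only before the dose.

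**The concern.** The scale asks how the volunteer feels at the moment of marking, so it cannot recover a feeling from the previous afternoon. Section 3.2.2 names somnolence and dizziness among the side effects of SQL SR. Several of the 16 lines bear on these, for example alert-drowsy, muzzy-clear headed and lethargic-energetic. Yet the only on-drug ratings come just before the next dose, when quetiapine is near its lowest.

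Vital signs are taken both before the dose and near the peak on most treatment days, while the VAS is taken only before it. Secondary objective 2 is not limited to carry-over into the next morning, and the schedule can deliver nothing else. Small VAS changes would say little about how volunteers felt at the exposure at which NET occupancy is measured.

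**Working it through.** **1. The plan's own peak-timed window.** Tracer injection is at 3.5 h post-dose (Table 1, footnote i). Data sampling starts 90 min after injection and lasts 120 min (Section 4.2.3.3).
- Start: 3.5 + 1.5 = 5.0 h
- End: 5.0 + 2.0 = 7.0 h

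This reproduces the stated 5-7 h and brackets the 6 h peak.

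**2. When the VAS falls (Panel A).** There are eight daily doses, Days 1-8.
- Day -1 is training and Day 1 is the pre-dose baseline. Both precede any tablet.
- The on-drug ratings are the pre-dose ones on Days 2-8 (seven) and the discharge rating on Day 9 (one), eight in all.
- The lead before the next dose is not stated. I assume 15 min to 2 h, so the lag from the previous tablet is 24 - 0.25 = 23.75 h down to 24 - 2 = 22 h, and about 24 h on Day 9.
- From the 6 h peak, this is 22 - 6 = 16 h to 24 - 6 = 18 h.
- Ratings between dosing and 12 h post-dose: none.

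**3. Quetiapine at the rating relative to peak, simple decay.** Ratio = 2^(-(t - 6)/t½). The protocol gives two half-lives. Section 1.1: "The elimination half-life of quetiapine is approximately 7 hours for both formulations". Section 3.2.1 gives a half-life that "is 6 hours post-dose".

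| Time since tablet | t½ = 6 h | t½ = 7 h |
|---|---|---|
| 24 h | 2^(-18/6) = 0.125 | 2^(-18/7) = 0.168 |
| 22 h | 2^(-16/6) = 0.157 | 2^(-16/7) = 0.205 |

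**4. Sensitivity to continued absorption.** Simple decay from 6 h ignores tablet still being absorbed after the peak. As an assumption, take a one-compartment model at steady state with first-order absorption and a 24 h interval:

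C(t) ∝ e^(-kt)/(1 - e^(-24k)) - e^(-ka·t)/(1 - e^(-24ka)), with k = ln 2/t½ and ka solved so that Tmax = 6 h.
- t½ = 6 h: ka = 0.187 per h, C(24)/C(6) = 0.272
- t½ = 7 h: ka = 0.206 per h, C(24)/C(6) = 0.301

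At 24 h, the range over both models is therefore about 12% to 30% of peak.

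**5. NDAQ.** The protocol gives a Tmax of 6 h for this active metabolite but no half-life, so its level at the rating cannot be calculated.

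**The case against.** The strongest reply is that nothing here is inconsistent. Tables 1 and 2, Section 4.4.4 and the amended tables all agree. Secondary objective 2 asks for change in VAS and promises no peak effect. A Day 1 pre-dose baseline followed by daily pre-dose ratings does yield a change measure, and one matched for time of day. This stands: the point concerns a design choice and is not an error or a contradiction.

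Three stronger readings are tempting, and the protocol does not support them.
- *Peak sedation goes unrecorded.* Volunteers are confined throughout dosing, and Section 4.7.1.2 collects adverse events from spontaneous report, an open question and observation. What is missing is a graded self-rating near the peak.
- *The scale is a sedation measure.* Section 4.4.4 describes it as assessing self-rated feelings, and its lines include happy-sad and contented-discontented.
- *A flat VAS would be reported as no subjective effect.* The analysis is descriptive, with three volunteers per panel and no power calculation (Sections 6.3.3 and 6.3.4). No section plans a test or announces such a conclusion.

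Two objections concern the remedy. A rating at 6 h (about 15:00 after a dose at about 9 am) compared with a morning baseline would mix time of day with drug effect in an open-label study without placebo. That is right, and an added rating needs its own undosed reference at the same clock time. Also, a rating on a non-PET day has no same-day occupancy or plasma profile, because PK sampling takes place on the PET 2 day only. That limit remains: the volunteer is in the scanner at 6 h on that day.

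**Conclusion.** The point holds as a minor, easily improved design choice. In Panel A, all eight on-drug VAS ratings fall about 22-24 h after the previous tablet and none falls near the peak, while vital signs on non-PET treatment days, the maintenance ECG and PET are timed to it. As scheduled, the scale can show residual next-morning effect only.

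At 24 h, quetiapine is roughly 12-17% of peak by simple decay or 27-30% in the one-compartment model. The first range rests on the protocol's half-lives and no absorption after 6 h, the second on an assumed absorption model. A reader might infer that volunteers are almost drug-free at the rating. The documents do not support this, because the higher range is plausible for a sustained-release tablet and NDAQ at that time is unknown. The conclusion about timing does not depend on which range is right. No primary endpoint is affected.

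**What to change.** In Table 1 footnote k and Section 4.4.4 (and in the reissued Table 1 of the amendment):
- Keep the pre-dose VAS and describe it as a measure of residual next-morning effect.
- Add a VAS at 6 h post-dose, with the vital signs already scheduled then, on selected non-PET days. Examples are the first day of each dose level and the third maintenance day. In Panel A these are Days 1, 3, 5 and 7, with the ECG already due at 6 h on Day 7.
- Add one undosed rating at the same clock time on Day -1, after the training session.
- Summarise separately the trough change from the Day 1 pre-dose baseline and the 6 h change from the time-matched Day -1 rating.

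In Panel A this example adds 4 + 1 = 5 questionnaires per volunteer: a few minutes each and a few extra CRF pages, in people already confined and already seen at 6 h on those dosing days. Admission on Day -1 must be early enough to allow the afternoon rating. If the sponsor prefers not to add ratings, stating in Section 4.4.4 that the scale addresses residual effect only would at least make its scope clear.
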